7.8 Other Baseline Characteristics

All other baseline characteristics, as listed below, at screening and on admission (unless otherwise stated) will be listed:

- Carbon monoxide breath test
- Urine drug screen
- Alcohol breath test
- SARS-CoV-2 Antigen test (if required See detail in Appendix 1)
- Virology (screening only)
- eGFR (screening only)

8 Efficacy

Not applicable.

9 Mass Balance

9.1 Mass Balance Parameter Estimation

Pharmaron will provide the following concentration and weight data on a per subject basis for each collection interval as specified in the clinical protocol:

- Total radioactivity concentration for urine and faeces (mass unit equivalents/g)
- Weight of urine (g)
- Faeces weight (g) i.e. not faecal homogenate weight

Concentration values will be expressed in terms of mass unit equivalents of the free base form. Quotient Data Sciences will be responsible for the calculation of excretion and recovery of total radioactivity in urine, faeces and urine and faeces combined for inclusion into the clinical study report. For the purposes of this document "excretion" will be used when describing the amount of total radioactivity excreted and "recovery" will be used when describing the amount of total radioactivity expressed as a percentage of the radioactive dose administered.

9.1.1 Definition of Mass Balance Parameters

A list of mass balance parameter definitions is provided in Table 2.

Parameter	Definition	Units	DP or SF	No. of DP/SF
Ae(urine)	amount of total radioactivity excreted in urine	Mass unit equiv	SF	3
%Ae(urine)	amount of total radioactivity excreted in urine expressed as a percentage of the radioactive dose administered	%	DP	2
CumAe(urine)	cumulative amount of total radioactivity excreted in urine	Mass unit equiv	SF	3
Cum%Ae(urine)	cumulative amount of total radioactivity excreted in urine expressed as a percentage of the radioactive dose administered	%	DP	2
Ae(faeces)	amount of total radioactivity eliminated in faeces	Mass unit equiv	SF	3
%Ae(faeces)	amount of total radioactivity eliminated in faeces expressed as a percentage of the radioactive dose administered	%	DP	2
CumAe(faeces) cumulative amount of total radioactivity eliminated in faeces		Mass unit equiv	SF	3
Cum%Ae(faeces)	faeces) cumulative amount of total radioactivity eliminated in faeces expressed as a percentage of the radioactive dose administered		DP	2
Ae(total)	amount of total radioactivity excreted in urine and faeces combined	Mass unit equiv	SF	3
%Ae(total)	amount of total radioactivity excreted in urine and faeces combined expressed as a percentage of the radioactive dose administered	%	DP	2

 Table 2
 Mass Balance Parameters and Reporting Specifications

Parameter	Definition	Units	DP or SF	No. of DP/SF
CumAe(total)	cumulative amount of total radioactivity excreted in urine and faeces combined	Mass unit equiv	SF	3
Cum%Ae(total)	cumulative amount of total radioactivity excreted in urine and faeces combined expressed as a percentage of the radioactive dose administered	%	DP	2

Home collections of urine and/or faeces may be requested at the discretion of the investigator for individual subjects. For amount excreted and cumulative excretion this will be calculated for all time points including home collection, if applicable.

Dose will be used in the calculation of mass balance parameters as per Table 3.

Table 3 Mass Balance Dose Specifications

Radioactive dose level for mass balance analysis	Actual	
Precision	As provided by Pharmaron	

9.1.2 Rules for Mass Balance Parameter Estimation

The following will be calculated for total radioactivity in urine, faeces and urine and faeces combined by Quotient Data Sciences (note that the amount excreted in pre-dose samples will not be included in the calculation of the cumulative amount excreted or in the calculation of the cumulative percentage of the radioactive dose excreted):

• The amount excreted in urine i.e. Ae(urine) and the amount excreted in faeces i.e. Ae(faeces) will be calculated for each collection interval the following formula (where matrix is either urine or faeces): using

Following Day 26, where urine/faecal collections are no longer continuous and return visits (i.e., Day 28 [±2 days] and Day 35 [±2 days]) are scheduled, additional interpolation of A_e will be calculated to estimate amount excreted on non-collection days (i.e., between Day 26 to Day 28, and Day 28 to Day 35 if required), as follows:

where Day x and Day y are the calculated amounts excreted for the preceding and proceeding days of the interval to be calculated.

Interpolation may also be calculated to estimate the amount excreted between home collects if required.

• The total amount excreted in urine and faeces combined, i.e. Ae(total), will be calculated for each collection interval using the following formula:

- The cumulative amount excreted in urine i.e. CumAe(urine) and the cumulative amount excreted in faeces i.e. CumAe(faeces) will be calculated by the incremental summation of the Ae(<matrix>) across all collection intervals (where matrix is either urine or faeces). The amount excreted in the pre-dose sample should not be included in the calculation of the cumulative amount excreted.
- The cumulative amount excreted in urine and faeces combined i.e. CumAe(total) will be calculated across all collection intervals using the following formula:

• The % amount of the total radioactive dose excreted in urine i.e. %Ae(urine) and the % amount of the total radioactive dose excreted in faeces i.e. %Ae(faeces) will be calculated for each collection interval using the following formula (where matrix is either urine or faeces):

%Ae(<matrix>) = 100 * Ae(<matrix>) / Total Radioactive Dose Administered

• The % amount of the total radioactive dose excreted in urine and faeces combined will be calculated for each collection interval using the following formula:

- The cumulative % amount of the total radioactive dose excreted in urine i.e. Cum%Ae(urine) and the cumulative % amount of the total radioactive dose excreted in faeces i.e. Cum%Ae(faeces) will be calculated by the incremental summation of the %Ae(<matrix>) across all collection intervals (where matrix is either urine or faeces). The % amount of the total radioactive dose excreted in the pre-dose sample should not be included in the calculation of the cumulative % of dose excreted.
- The cumulative % amount of the total radioactive dose excreted in urine and faeces combined will be calculated for each collection interval using the following formula:

For urine and faeces, where a subject has failed to void over a particular collection interval the Amount Eliminated (Ae) will be set to zero.

If part of a void over a particular collection interval is missing due to spillage or accidental discarding, the Ae will still be calculated providing other samples have be collected within the interval. Where no other samples are collected within the interval the data will be set to missing for the purposes of the calculation of Ae, CumAe and Cum%Ae. In both scenarios the data will be flagged to highlight a missing void.

Imputation of non-numerical values reported in the urine and faecal data set (i.e. concentrations that are not detectable [ND] below the limit of quantification [BLQ]) will be entered as zero for calculation of parameters such as Ae.

When converting urine collection weights to urine volume (if required), the following conversion factor will be used:

1.02 g of urine = 1 mL of urine

This will be calculated in SAS as follows:

Urine weight (g) / 1.02 = Urine volume (mL)

If total radioactivity concentrations in urine have been provided in mass unit/g units the following conversion (if required) will be performed using SAS:

Concentration (mass units/g) * 1.02 = Concentration (mass units/mL)

The radioactivity associated with toilet paper may be determined with the approval of Hepion. The results will be reported for each subject as a single value for the whole collection period and included in the calculation of total amount excreted and % of dose recovered.

Accidental sources of elimination, e.g., vomiting, will be collected and sent for total radioactivity analysis. This will be reported on a case by case basis and details will be included in the documentation of the mass balance population.

9.2 Mass Balance Summary Tables

Summary statistics (i.e. n, mean, SD, coefficient of variation [CV%], minimum, median and maximum) will be presented for amount excreted (Ae) and recovery (%Ae) by collection period for the following:

- Urine [i.e. Ae(urine) and %Ae(urine)] for total radioactivity
- Faeces [i.e. Ae(faeces) and %Ae(faeces)] for total radioactivity
- Urine and faeces combined [i.e. Ae(total) and %Ae(total)] for total radioactivity

In addition, summary statistics (i.e. n, mean, SD, CV%, minimum, median and maximum) will be presented for the cumulative excretion and cumulative recovery by collection period for each of the following:

- Urine [i.e. CumAe(urine) and Cum%Ae(urine)] for total radioactivity
- Faeces [i.e. CumAe(faeces) and Cum%Ae(faeces)] for total radioactivity
- Urine and faeces combined [i.e. CumAe(total) and Cum%Ae(total)] for total radioactivity

Finally, summary statistics (i.e. n, mean, SD, CV%, minimum, median and maximum) will be presented for the cumulative excretion and cumulative recovery for the study as a whole for each of the following:

- Urine [i.e. CumAe(urine) and Cum%Ae(urine)] for total radioactivity
- Faeces [i.e. CumAe(faeces) and Cum%Ae(faeces)] for total radioactivity
- Urine and faeces combined [i.e. CumAe(total) and Cum%Ae(total)] for total radioactivity

If any subject withdraws prior to the end of a study visit or if subjects have differing collection intervals [(e.g. Day 10 for some subjects and Day 14 for others)] then a last observation carried forward (LOCF) approach will be used whilst calculating cumulative Ae and %Ae (i.e. CumAe and Cum%Ae), where the last observed value will be carried forward to the subsequent time point. The number of subjects included at each collection

interval will therefore remain the same regardless of subject withdrawals. The LOCF approach will be used for all summary tables detailed above.

9.3 Mass Balance Figures

Mean balance figures will be presented for the mass balance population.

Mean cumulative excretion (i.e. CumAe) and cumulative recovery (i.e. Cum%Ae) vs time curves will be produced on a linear/linear scale and will include ± SD bars. These plots will be produced for CumAe and Cum%Ae, respectively, with urine, faeces and total overlaid:

- Urine [i.e. CumAe(urine) and Cum%Ae(urine)] for total radioactivity
- Faeces [i.e. CumAe(faeces) and Cum%Ae (faeces)] for total radioactivity
- Urine and faeces combined [i.e. CumAe(total) and Cum%Ae(total)] for total radioactivity

A legend identifying each profile (i.e. urine, faeces and total) will be displayed on the mean plots. Figures will be produced using the LOCF imputation strategy (see Section 9.2) if summary tables are produced using this method (a footnote to indicate this will be added to figures as required).

9.4 Mass Balance Listings

The sample collection data (e.g. collection intervals) for all urine and faecal samples will be listed. In addition all total radioactivity concentrations, urine and faecal weights and all mass balance parameters will be listed on a per subject basis. The LOCF approach will be used for all cumulative mass balance parameters. Where LOCF values appear in the listings they will be flagged.

9.5 Statistical Analysis of Mass Balance Parameters

No formal statistical analysis will be performed for the mass balance data in this study. Descriptive statistics (i.e. n, mean, SD, median, CV%, minimum and maximum) are considered adequate for a study of this type.

10 Pharmacokinetics

10.1 Plasma and Whole Blood PK Parameter Estimation

The PK parameters for rencofilstat in whole blood and total radioactivity in plasma and whole blood will be estimated where possible and appropriate for each subject profile by non-compartmental analysis methods using Phoenix WinNonlin software (v8.3 or a more recent version, Certara USA, Inc., USA). Additional parameters may be calculated if required, depending on the data.

10.1.1 Definition of Plasma and Whole Blood PK Parameters

Plasma and whole blood PK parameter definitions are provided in Table 4.

Table 4Plasma and whole blood PK Parameter Definitions and Rounding
Specifications

Parameter	Definition	Unit	DP or SF	No. of DP/SF
Tlag	Time prior to the first measurable concentration	h	DP	2

Parameter	Definition	Unit	DP or SF	No. of DP/SF
Tmax	Time of maximum observed concentration	h	DP	2
Cmax	Maximum observed concentration	mass unit/mL	SF	3
AUC(0-24)	Area under the curve from time 0 to 24 h post-dose	Mass unit.h/mL	SF	3
AUC(0-last)	Area under the curve from time 0 to the time of last measurable concentration	mass unit.h/mL	SF	3
AUC(0-inf)	Area under the curve from time 0 extrapolated to infinity	mass unit.h/mL	SF	3
AUCextrap	Area under the curve (AUC) from time of the last measurable concentration to infinity as a percentage of the area under the curve extrapolated to infinity	%	DP	2
T1/2	Terminal elimination half-life	h	DP	2
lambda-z	First order rate constant associated with the terminal (log-linear) portion of the curve	1/h	DP	4
CL/F	Total body clearance calculated after a single extravascular administration where F (fraction of dose bioavailable) is unknown.	mL/min	SF	3
Vz/F	Apparent volume of distribution based on the terminal phase calculated using AUC(0-inf) after a single extravascular administration where F (fraction of dose bioavailable) is unknown	L	SF	3
MRT(0-last)	Mean residence time from time 0 to time of the last measurable concentration	h	DP	2
MRT(0-inf)	Mean residence time 0 extrapolated to infinity	h	DP	2
AUC Ratio	Parent to total radioactivity ratio for whole blood based on AUC(0-inf)	NA	DP	2
lambda-z lower*	Lower limit on time for values to be included in the calculation of lambda-z	h	DP	2
lambda-z upper*	Upper limit on time for values to be included in the calculation of lambda-z	h	DP	2

DP=decimal places

SF=significant figures

*=these values should be listed but omitted from the descriptive statistics NA=not applicable

Dose will be used in the calculation of relevant PK parameters as per Table 5.

Table 5 PK Parameter Dose Specifications

Dose Route	Nominal/Actual	Precision
Oral	Nominal	As per Protocol

Total radioactivity blood to plasma concentration ratios will be determined using SAS by the Lead Statistical Programmer (or designee) at the time points defined in the protocol. If either the blood or plasma concentration values are BLQ (i.e., <lower limit of quantification [LLOQ]) at any given timepoint the ratio will not be calculated.

When converting blood collection weights to blood volume (if required) for the calculation of the whole blood:plasma ratio, the following conversion factor will be used:

1.06 g of blood = 1 mL of blood

This will be calculated in SAS as follows:

Alternatively, where total radioactivity concentrations in blood have been provided in mass unit/g units the following conversion will be performed using SAS:

Concentration (mass units/g) * 1.06 = Concentration (mass units/mL)

In addition, the ratio of rencofilstat to total radioactivity in whole blood will be calculated based on AUC using AUC(0-inf):

AUC ratio = $\left\{\frac{AUC(reconfilstat)}{AUC(total radioactivity)}\right\}$

If for any reason the AUC(0-inf) is not calculable then an alternative or additional AUC over a partial area may be used to calculate the AUC ratio for all subjects.

10.1.2 Rules for Plasma and Whole Blood PK Parameter Estimation using WinNonlin

The imputation of non-numerical (e.g. below the limit of quantification [BLQ] or below the level of detection [LOD]) or negative values (e.g. pre-dose sampling times) reported in the input data set will be performed as follows for calculation of PK parameters:

- Predose sample times will be entered as zero
- Values that are BLQ* obtained prior to Cmax will be entered as zero and values that are BLQ* after Cmax will be treated as missing
- Values that are BLQ* after Cmax may be imputed as zero for the calculation of partial AUCs, in cases where lambda-z cannot be determined
- Values that are measurable after at least 2 consecutive BLQ* values after Cmax will be treated as missing for the calculation of PK parameters
- Values that are reported as "No Result" or "Not Reportable" (NR), "Not Calculated" (NC) or "No Sample" (NS) etc. will generally be considered missing
- * values that are reported as below the LOD will be treated in the same way as samples reported as BLQ.

Missing or unusual concentration values in the input data may be queried to ascertain any underlying cause. Exclusion of missing or unusual concentration values, or repeat bioanalysis of samples, will only be performed if a definitive root cause can be established and approval from Hepion has been obtained. Any exclusions of concentration values or repeat analysis of samples will be documented appropriately.

Plasma and whole blood PK parameters will be estimated using standard Phoenix WinNonlin methods, details of which may be found in the documentation accompanying the WinNonlin software package. The rules specified in Table 6 will be applied:

Sampling times	Actual
Calculation method	Linear trapezoidal linear interpolation
Number of points used for lambda-z	At least 3, not including Cmax
Minimum requirements for AUC	At least 3 consecutive measurable concentrations

Table 6 PK Parameter Estimation Details

Prior to PK parameter estimation the bioanalytical data may be corrected to account for the proportion of administered ¹⁴C material not measured due to the use of a ¹²C LC-MS/MS analysis method. Data correction will only be performed if the ¹⁴C contribution exceeds 1 % of the dose administered. Bioanalytical data will be multiplied by the determined data correction factor in SAS by the lead statistical programmer (or designee).

Where possible, the terminal elimination rate constant (lambda-z) will be calculated for all subject profiles. The value of lambda-z will be determined by the slope of the regression line of the natural log transformed concentrations vs time.

The WinNonlin determined choice of data points for determination of lambda-z will be reviewed by the pharmacokineticist who may adjust the selection in order to provide a more appropriate fit. The choice of data points for determination of lambda-z for each profile will be confirmed following a documented peer review.

10.1.3 Plasma and Whole Blood PK Parameter Reporting Specifications

The following parameters will be reported for each period as applicable, according to the rounding specifications provided in Table 4:

Tlag, Tmax, Cmax, AUC(0-24), AUC(0-last), AUC(0-inf), AUCextrap, T1/2, lambda-z, CL/F (Rencofilstat only), Vz/F (Rencofilstat only), MRT(0-last), MRT(0-inf), AUC ratio (Rencofilstat only), lambda z lower and lambda z upper

The flags/footnotes given in Table 7 will be applied to the PK parameters where relevant and will be shown in PK parameter listings. Additional flags may be applied based on emerging data.

Flag	Footnote	
а	Adjusted rsq of regression (the goodness of fit statistic for the elimination phase) was <0.9	
b	Period used for regression analysis was less than 2-fold the calculated half-life	
С	Extrapolated portion of AUC(0-inf) >20%	
d	Insufficient post-Cmax data points for estimation of lambda-z	
е	e Entire profile BLQ, no PK parameters could be calculated	
f	Fewer than 3 consecutive measurable concentrations, AUCs not calculated	

Table 7PK parameter Flags and Footnotes

In the event that the adjusted rsq of regression was <0.9 ("a" flag) then lambda-z and parameter estimates derived using lambda-z and AUC(0-inf) will be deemed unreliable and will be flagged and listed but excluded from the summary statistics.

In the event that the time period used for regression analysis was less than 2-fold the calculated half-life ("b" flag) lambda-z and parameter estimates derived using lambda-z will be flagged, listed, and included in summary statistics.

In the event that the extrapolated portion of AUC(0-inf) >20% ("c" flag), then AUC(0-inf) and parameter estimates derived using AUC(0-inf) will be deemed unreliable and will be flagged and listed but excluded from the summary statistics.

In the event that there are insufficient post-Cmax data points for estimation of lambda-z ("d" flag) then lambda-z and parameter estimates derived using lambda-z and AUC(0-inf) will be reported as 'NC'.

In the event that there are fewer than 3 consecutive measurable concentrations ("f" flag) then all AUC parameter estimates will be reported as 'NC'.

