10.2 Concentration and PK Parameter Summary Tables

Summary statistics (i.e. n, mean, SD, CV%, median, minimum, maximum, geometric mean, geometric SD and geometric CV%) of concentration data will be calculated for the following analytes/matrices. The number of BLQ values (n) per time point will also be presented. Geometric statistics will not be calculated for pre-dose concentrations.

- Whole blood concentrations of rencofilstat by time point
- Plasma concentrations of total radioactivity by time point
- Whole blood concentrations of total radioactivity by time point
- Whole blood:plasma concentration ratios of total radioactivity by time point

Summary statistics (i.e. n, mean, SD, CV%, median, minimum and maximum) of whole blood PK parameters will be calculated for rencofilstat and total radioactivity. Geometric mean, geometric SD and geometric CV% will be presented for all PK parameters except Tlag and Tmax.

Non-measurable values reported in the concentration data (i.e., values that are BLQ), will be entered as zero for the determination of summary statistics with the exception of geometric means, geometric SD and geometric CV%, where BLQ values will be imputed as half the LLOQ value. This also applies to any concentrations that are defined as PK parameters (e.g., C24). Data recorded as NR, NS or NC will be handled as missing (i.e., no assumption will be made about the actual concentration).

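### The SAP's >20% extrapolation rule, as written, drops AUCextrap from its own summary, so the summarised values cannot exceed 20% (minor wording fix)

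*SAP*

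**What the plan says.** Four parts of the SAP combine.

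- **The trigger.** The 'c' paragraph of SAP 10.1.3 begins "In the event that the extrapolated portion of AUC(0-inf) >20" per cent.
- **The consequence.** The same sentence continues: "then AUC(0-inf) and parameter estimates derived using AUC(0-inf) will be deemed unreliable and will be flagged and listed but excluded from the summary statistics".
- **The definition.** SAP 10.1.1, Table 4, defines AUCextrap as the area "from time of the last measurable concentration to infinity as a percentage of the area under the curve extrapolated to infinity".
- **What is summarised.** SAP 10.1.3 includes AUCextrap in the reported set: "Tlag, Tmax, Cmax, AUC(0-24), AUC(0-last), AUC(0-inf), AUCextrap, T1/2, lambda-z" and so on. The Table 4 footnote "these values should be listed but omitted from the descriptive statistics" is attached only to the lower and upper time limits for lambda-z. SAP 10.2 adds: "Geometric mean, geometric SD and geometric CV% will be presented for all PK parameters except Tlag and Tmax". So AUCextrap is meant to appear in the summary tables.

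Neither 10.1.3 nor 10.2 exempts AUCextrap from the 'c' exclusion. Excluded values are still listed by subject with their flags (SAP 10.1.3 and 10.4).

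**The concern.** AUCextrap tells the reader how much of AUC(0-inf) was observed and how much was projected. That matters here because the parent-to-total-radioactivity AUC ratio in whole blood is a primary endpoint and is based on AUC(0-inf) by default (SAP 4 and 10.1.1). Withholding AUC(0-inf), CL/F or Vz/F when extrapolation is large has a reliability rationale. Withholding the measure of extrapolation on the same ground does not, because a large value is exactly what it exists to show. A summary cut off at the flag threshold cannot tell the reader that the threshold was often crossed.

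**Working it through.** **Step 1: logic.** By Table 4, AUCextrap = 100 × [AUC(0-inf) − AUC(0-last)] / AUC(0-inf). It is therefore a parameter derived using AUC(0-inf). The 'c' trigger is AUCextrap > 20%, and the 'c' consequence removes every such parameter from the summary. So an AUCextrap value is retained only if it is 20% or less, and every mean, median and maximum of the retained values is at most 20%, whatever the data.

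**Step 2: is extrapolation above 20% plausible for this drug?** Protocol Table 2 (225 mg, N=6, followed for 6 days) gives mean AUC(0-last) 53530 and mean AUC(0-inf) 80030 ng.hr/mL. One minus the ratio of means is 1 − 53530/80030 = 33.1%. A mono-exponential check with half-life 98.14 h gives 2^(−144/98.14) = 36.2%. With short sampling, yes.

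**Step 3: is it likely here?** Planned blood sampling runs to 504 h. Assuming a mono-exponential tail, the extrapolated fraction is 2^(−tlast/T½).

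- Parent, T½ 98.14 h, sampled to 504 h: 2^(−504/98.14) = 2.8%. No flag.
- Half-life at which 504 h leaves 20%: 504 × ln 2 / ln 5 = 217 h.
- Last measurable time below which parent exceeds 20%: 98.14 × ln 5 / ln 2 = 228 h.
- Total radioactivity: the documents give no half-life. Assumed values of 150, 200, 250 and 300 h give 9.7%, 17.4%, 24.7% and 31.2% at 504 h.

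Early stopping is possible: Protocol 8.1 ends all sample collection, blood included, once the whole group meets the mass balance criteria.

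**Step 4: size of the distortion if the rule bites.** I rebuilt the parent tail from Table 2:

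- k = ln 2/98.14 = 0.007063 per h
- C144 = (80030 − 53530) × k = 187 ng/mL
- C48 = 187 × 2^(96/98.14) = 369 ng/mL
- AUC(0-48) = 53530 − (C48 − C144)/k = 27,825 ng.hr/mL (unrounded concentrations)

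Holding C48 and AUC(0-48) fixed and drawing the half-life from N(98.14, 17.96), AUCextrap at time t is (C48/k) × exp[−k(t − 48)] / [27,825 + C48/k], with k now the drawn rate:

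| Last measurable sample | Mean, all profiles | Share above 20% (dropped) | Mean of retained values | Chance all six dropped (share^6) |
|---|---|---|---|---|
| 168 h | 27.6% | 89% | 16.5% | 49% |
| 192 h | 23.3% | 72% | 16.1% | 14% |
| 216 h | 19.7% | 49% | 15.4% | 1.5% |
| 504 h | 2.8% | 0% | 2.8% | 0% |

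From 216 h back to 168 h the mean over all profiles rises by about 8 points, while the displayed mean rises by about 1.

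**Step 5: a six-subject illustration (assumed values).** For 8, 12, 16, 19, 26 and 35%, the full summary is n=6, mean 19.3%, maximum 35%. Under the rule as written it is n=4, mean 13.8%, maximum 19%. If all six values are 20% or below, the two summaries are identical.

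**The case against.** The case for leaving the text alone has real weight.

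- **Nothing is suppressed.** Values above 20% are listed by subject with the 'c' flag, and the mock parameter table starts with n. With six subjects a reader can recover the full picture. In the 168 h scenario about half of such studies would show n=0, which reassures nobody. A reader might infer that the plan conceals heavy extrapolation; the documents do not support that. This stands, and it confines the problem to the summary tables. It does not remove it: the mock table's footnotes say nothing about exclusions, so a reduced n does not show whether 'a', 'c' or a missing estimate was the cause.
- **The truncated summary is coherent.** 'c' also removes AUC(0-inf) and the ratio based on it, so AUCextrap over the remaining profiles describes the AUC(0-inf) values actually summarised. This is a fair presentational argument, but the SAP does not make it, and the table would carry no note that the summary is conditional.
- **The effect needs conditions that the plan does not expect.** With parent sampled to 504 h there is none. Early release is allowed, but nothing in the documents suggests that it is likely by Day 8 to 10. This stands.
- **A pharmacokineticist might keep AUCextrap in anyway.** Possibly. The SAP does not name it among the excluded parameters, so the outcome would depend on a reading made after the data are seen.

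The 'a' rule might seem to share the fault, since it also removes AUCextrap. It does not. That rule acts on an adjusted r-squared below 0.9, not on the size of AUCextrap, and a poor lambda-z fit makes AUCextrap itself unreliable.

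**Conclusion.** Wrong as written, but minor. The 'c' rule taken literally caps the AUCextrap summary at 20%. No other summarised parameter changes, and the individual values survive in the listings. The consequence depends on profiles exceeding 20% extrapolation: early group discharge, early loss of quantification, or a total-radioactivity half-life above about 217 h with sampling to 504 h. The modelled sizes rest on a mono-exponential tail, the Table 2 mean profile and a normal spread of half-lives. They cover parent only, because the documents give no half-life or quantification limit for total radioactivity.

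Two further inferences should not be drawn. First, the summary does not look best when sampling ends early: the displayed mean in the table above is 16.5% at 168 h against 2.8% at 504 h. What is lost is discrimination, not direction. Second, the 33% from the earlier 225 mg group is one minus a ratio of group means under 6-day sampling. It is not a reported mean AUCextrap and does not predict this study.

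**What to change.** Add one sentence to the 'c' rule only: *AUCextrap is exempt from this exclusion and is summarised for every profile with an acceptable lambda-z* (calculable and not excluded under 'a'). In Tables 14.2.6.1 to 14.2.6.3, add a row giving the number of profiles whose AUC(0-inf) was excluded under 'c'. Leave the 'a' rule unchanged. Make the change before database lock, so that the choice does not follow the data.

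The cost is one sentence and one row per table, with no new data or sampling. The downside is that the AUCextrap summary may look less favourable and may cover more profiles than the AUC(0-inf) summary beside it; the count row explains the difference.
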